## **1. Study Objectives**

### **1.1 Primary Objectives**

The primary objectives of this study are to: (1) to determine whether 6 weeks of open-label placebo, double-blind placebo and no additional treatment control results in different clinical outcomes in patients with IBS and (2) assuming there are significant differences (a) to determine whether open-label placebo results in greater clinical improvement compared to no additional treatment control and (b) to determine if open-label placebo results in greater clinical outcome than double blind placebo.

### **1.2 Secondary Objectives**

- To confirm our previous finding that the COMT val158met polymorphism is associated with placebo response.
- To replicate our previous finding that certain personality traits (extraversion, agreeableness, openness) are associated with the placebo response in IBS.
- Using ethnographic interviews to obtain insight into patients' experiences, including their views of the clinical encounter.
- An exploratory objective of the study is to obtain pilot data to assess whether double-blind peppermint oil results in greater clinical improvement compared to double-blind placebo in patients with IBS.

## **2. Background and Rationale**

### **2.1 Background on IBS**

IBS is one of the top 10 reasons for seeing a primary care physician, and the symptoms of IBS are present in 7-15% of the North American population. IBS is a chronic functional gastrointestinal disorder that is not a disease since there is no definitive pathophysiology or biomarker. Endpoints in clinical trials with IBS are based on subjective responses and include abdominal pain, altered bowel habits and bloating. The average placebo response in randomized double-blind placebo controlled trials in IBS is approximately 41%, making IBS a particularly good population to study placebo. The explanation for the high placebo response in clinical trials such as IBS is unclear and attempts at reducing the placebo response in clinical trials have been largely unsuccessful. To date no studies have compared double-blind placebo to open-label placebo as proposed in this study. This information is critical to understanding the effects of placebo as it relates to the design of clinical trials. Likewise, this information is critical to clinical practice, since clinical practice is unblinded yet decisions are based on inferences made from blinded randomized controlled trials. Including both blinded and open-label arms will allow us to quantify, for the first time prospectively, the difference in efficacy between these kinds of administrations. Such knowledge will strengthen inferences on clinical practice that are based on blinded randomized controlled trials.

### **2.2 Study Rationale**

[figure not shown]
The vast majority of placebos are administered with concealment (i.e., blinded assignment in RCTs). Most clinicians and researchers believe that either deception or concealment is necessary to achieve a placebo response. To date, few studies have directly compared the effects of open-label placebo and double-blind placebo. We propose a novel, multi-disciplinary design to answer multiple clinical and research design questions concerning placebo effects.

### 3. Study Design

#### 3.1 Overall Design and Plan of the Study

This study aims to investigate the effects of open-label placebos with double-blind placebos as administered in a randomized controlled trial in a 6-week trial with 313 IBS patients on standard treatment for IBS randomly assigned to one of four arms:

- open-label placebo
- double-blind placebo
- double-blind peppermint oil
- no additional treatment control.

#### 3.2 Efficacy Assessments

##### Primary Outcome Measure

The primary outcome measure is the IBS symptom severity scale (IBS-SSS). The IBS-SSS is a questionnaire that measures the sum of the participant's evaluation on a 100 point scale of each of five items: severity of abdominal pain, frequency of abdominal pain, severity of abdominal distension, dissatisfaction with bowel habits, and interference with quality of life. All five components contribute equally to the score, yielding a theoretical range of 0-500, in which a higher score indicates a more severe condition. The responder will be considered a patient who has at least a 50 point decrease in their IBS-SSS from baseline to Visit 3. Using data from our previous IBS trial the calculated Cronbach's alpha is .70.

#### **4. Selection and Enrollment of Participants**

Approximately 313 IBS patients who meet all of the inclusion criteria and none of the exclusion criteria will be enrolled.

##### **4.1 Inclusion Criteria**

To be eligible for enrollment, male and female patients must meet all of the following inclusion criteria:

1. Provide signed and dated informed consent and understand the nature of the study sufficiently to allow completion of all study assessments.
2. Be ambulatory, community dwelling, 18 to 80 years, inclusive
3. Meet Rome IV diagnostic criteria for IBS
4. Have IBS of at least moderate severity, i.e., have a score on the IBS-SSS of  $\geq 175$  (0-500) at the baseline visit
5. If the patient is on medications which affect the gastrointestinal tract or visceral sensation (e.g., tricyclic antidepressants, fiber, antispasmodics, etc.), must be on a

stable dose for at least 1 month prior to entering the study and for the duration of the study.

#### **4.2 Exclusion Criteria**

If any of the following exclusion criteria are met, the patient is not eligible for the study:

1. Self-reported pregnancy or planned pregnancy within the next two months.
2. Have an established diagnosis of any concomitant bowel disturbance that would interfere with the assessment of efficacy or safety in the study (e.g., Hirschsprung's disease, diverticulitis, colonic ischemia).
3. Report warning symptoms (e.g., rectal bleeding, weight loss >10%, iron deficiency anemia, etc.) otherwise not explained
4. Have undergone previous abdominal surgery of the intestines (with the exception of uncomplicated appendectomy, cholecystectomy, hysterectomy, or polypectomy  $\geq$  6 months prior to enrollment).
5. Have a history of drug, excluding nicotine or caffeine, or alcohol abuse within 2 years of entry into the study
6. Exhibit abnormalities on physical examination, unless judged to be clinically insignificant by the Investigator. Such cases will be noted.
7. Current, within the past 30 days, therapeutic use of enteric coated peppermint oil for the treatment of IBS
8. Known or suspected peppermint or soybean oil allergy
9. Severe acid reflux (> 3 episodes of heartburn or regurgitation per day on average over a week)
10. Inability to speak or read English
11. Unable or unwilling to cooperate with the study protocol or considered by the Investigator to be unsuitable for the study.

#### **4.3 Screen Failures**

Patients will be allowed to rescreen once if they do not meet inclusion criteria #4 or #5 at the initial screening visit.

### **5. Study Interventions**

#### **5.1 Interventions, Administration, and Duration**

The study involves four groups as follows:

- open-label placebo 1 softgel TID (N~80)
- double-blind placebo 1 softgel TID (N~80)
- double-blind peppermint oil 1 softgel TID (N~40)
- no additional treatment control (N~80)

Placebo will be supplied as soybean oil (manufactured by SoftGel Technologies Inc.), matched to peppermint oil softgels (Pepogest™). The open-label and double-blind placebo are identical and both are matched to the peppermint oil. Each peppermint oil dose is 0.2mL. Study drug should be administered approximately 30 minutes before meal times.

#### **5.2 Concomitant Interventions**

Patients will be allowed to continue their IBS medications (e.g., fiber, anti-spasmodics, loperamide, etc.) as long as they had been on stable doses for at least 30 days prior to entering the study and agree not to change medications or dosages during the trial. Any non-pharmacological treatments for IBS (e.g. meditation, acupuncture, etc.) will be allowed as long

as they were on a stable pattern/behavior for at least 30 days prior to entering the study. All concomitant interventions will be recorded. Patients will be asked to refrain from making any major life-style changes (e.g., starting a new diet, changing their exercise pattern or starting a stress reduction program) during the study.

### 5.3 Study Drug Accountability

Accountability for the study drug will be the responsibility of the Research Pharmacy at Beth Israel Deaconess Medical Center. Drug accountability records indicating the study drug delivery date to the study center, inventory at the study center, and use by each subject will be maintained at the Research Pharmacy. These records will document that the subjects were provided the study drug as specified in the protocol.

All unused study drug will be retained at the study center.

## 6. Study Procedures

The study will consist of a screening telephone call no more than 60 days prior to the screening visit during which subjects will be assessed for study qualification. Eligible subjects will then undergo three visits – screening visit (baseline assessments and randomization will occur at this visit); midpoint visit; and endpoint visit.

### 6.1 Schedule of Evaluations

Assessment	Screening Visit	Week 3 (± 5 business days)	Week 6 (± 5 business days)
		Midpoint Visit	Endpoint Visit
Informed Consent Form	X		
Clinician Interaction	X	X	X
Demographics	X		
Medical History	X		
Inclusion/Exclusion Criteria	X		
Physical Exam	X	X	X
Vital Signs	X		X
Current Medications	X		
Randomization	X		
Blood for Genetic Analysis	X		X
Questionnaires	X	X	X
Concomitant Medications		X	X

Adverse Events		X	X
----------------	--	---	---

## 6.2 Description of Evaluations

Potential participants will be screened by telephone to determine if they meet the Rome IV Criteria for IBS and do not suffer from other active diseases or are on medications that would disqualify them for enrollment.

### 6.2.1 Enrollment, Baseline and Randomization

**Visit 1 (Baseline & Randomization):** The informed consent will clearly indicate that the study is testing placebo; it will also clearly indicate that the placebo pills are inert, “like sugar pills.” Subjects, who provide informed consent and fulfill the inclusion and exclusion criteria, including an IBS-SSS of at least 175, will be eligible to enter the trial. A research coordinator will assist in completion of questionnaires and collection of blood. A clinician with expertise in IBS will review the patient’s history, perform a physical exam and confirm the diagnosis of IBS. Subjects will be randomly assigned to one of the four groups. Randomization will be accomplished by using sequentially numbered opaque sealed envelopes provided to the clinician. All assessments with the exception of blood collection will occur prior to randomization.

Depending on the assignment, subjects will be given a semi-scripted discussion regarding their assignment. The clinician will make every effort to assure equal attention, encouragement and patient-clinician relationship.

Subjects in all groups will be reminded not to make changes to their diet, exercise, and IBS medications, which may be continued during the study, provided that they are on a stable dose for 1 month. Subjects will be told to return in 3 weeks. (Note: Approximately 42 patients will be randomly selected to participate in the nested qualitative study and will undergo a detailed interview at the conclusion of Visit 3).

Subjects will be instructed on the completion of the daily diary to be completed nightly for the seven days prior to both Visit 2 and Visit 3.

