### 6.2.3 Sample Collection

Genetic variation in genes encoding proteins involved in several neurotransmitter pathways has been shown to modify response to placebo treatment. This study will build on these findings to examine how placebo treatment modifies gene, protein and miRNA expression as well as changes in metabolism that may be associated with differential response to placebo treatment.

Although all these genomic studies will not be run in the primary study, it is important to collect samples that will allow these analyses to be done in the future. Aliquots of plasma, serum, white cells and red cells will be de-identified and stored at -80C. Samples will be collected at baseline and at the end of the study.

GWAS will be conducted to identify genes implicated in modifying placebo response.

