### **9.3 Protocol Deviations/Violations**

If a subject does not complete a daily diary entry, it will not be considered a protocol deviation/violation. If blood is not obtained at either Visit 1 or Visit 3, it will not be considered a protocol deviation/violation.

## Appendix 1

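### The Visit 1 blood sample labelled baseline is not required to precede randomisation, so later change-from-baseline analyses of expression and metabolism lack a protected baseline

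*Combined protocol and SAP*

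**What the plan says.** Screening, baseline measurement and randomisation share one visit; Section 6 says "baseline assessments and randomization will occur at this visit". Within that visit, Section 6.2.1 fixes the order for everything but blood: "All assessments with the exception of blood collection will occur prior to randomization". The next step it describes is specific to the arm: "Depending on the assignment, subjects will be given a semi-scripted discussion regarding their assignment".

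Section 6.2.3 treats the first sample as the pre-treatment reference: "Samples will be collected at baseline and at the end of the study". Its stated scientific purpose is to "examine how placebo treatment modifies gene, protein and miRNA expression as well as changes in metabolism". It adds that the genomic work will not all be done within the primary study and that aliquots are stored for later use.

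The table in Section 6.1 lists "Blood for Genetic Analysis" at the screening visit and at Week 6, and Appendix 3 likewise has blood at Visits 1 and 3. Neither gives an order within the visit.

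**The concern.** A baseline for measuring change should be taken before anything that differs by arm. In many drug trials, blood drawn after assignment but before the first dose would do little harm, because the exposure is the drug. Here the exposure includes what the patient is told. Section 5.1 makes the open-label and double-blind placebo softgels identical, so those two arms differ only in the information given. Patients in the open-label and no-treatment arms learn their arm at Visit 1, and patients in the blinded arms learn that they are in a blinded arm.

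If blood is taken after that disclosure, any acute response to it becomes part of the reference value and is subtracted from the later change. At stake is the use of stored samples to study change under placebo. A pre-assignment sample cannot be collected afterwards, so the order matters even though the laboratory work is partly deferred.

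**Working it through.** The plan gives no figure to reproduce: it states no effect size, variance or sample size for expression or metabolic markers. The check compares the passages and then uses simple algebra.

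**Order of events**

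1. Section 6.2.1 exempts blood from the pre-randomisation rule. The natural reading is a draw after randomisation; at the least, an earlier draw is not required.
2. Earlier in the same section, before randomisation is mentioned, stands "A research coordinator will assist in completion of questionnaires and collection of blood". It gives no time, and the explicit sentence on order comes later and singles out blood. If an earlier draw was intended, the two sentences conflict.
3. The arm-specific discussion comes after assignment. Nothing places the draw before it.
4. The time of the first dose relative to the draw is not stated, and no recording of the draw time is required.
5. Section 6.2.3 still labels the sample baseline.

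So the first sample may precede or follow the discussion, and the data would not show which.

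**Effect on a change score**

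Let Y0 be an arm's mean marker level before assignment, Y6 its mean at Week 6, and a the mean shift between assignment and draw. The true change is D = Y6 − Y0. The first sample measures Y0 + a, so the measured change is D − a. Writing a = fD gives (1 − f)D. The documents give no f; the values below are assumptions:

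- f = 0: measured change D, no bias.
- f = 0.1: 0.9D, 10% too small.
- f = 0.3: 0.7D, 30% too small.

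**Effect on a comparison of arms A and B**

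Measured contrast = (D_A − a_A) − (D_B − a_B) = (D_A − D_B) − (a_A − a_B), so the bias is −(a_A − a_B).

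- With the same f in both arms, the contrast is (1 − f)(D_A − D_B): it shrinks but keeps its sign.
- With equal true change D in both arms, f_A = 0.3 and f_B = 0, the measured contrast is 0.7D − D = −0.3D although the truth is zero.
- With covariate adjustment for the first sample, slope b, the bias is −b(a_A − a_B).
- With Week 6 values alone, randomisation makes the arms' Y0 equal in expectation. The contrast then estimates D_A − D_B, and a does not enter.

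**Which contrasts are exposed**

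Under Section 6.2.4 the clinician does not know which double-blind patients receive peppermint oil, so the discussion cannot differ between those two arms. Their shifts are equal in expectation if the draw precedes the first dose, and the difference in change between them is then unbiased. The exposed contrasts are those among open-label placebo, no treatment and the blinded arms, together with change within any one arm.

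**How many samples**

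The rule covers every Visit 1 sample: 80 + 80 + 40 + 80 = 280 by the approximate arm sizes in Section 5.1, or 313 by Sections 3.1 and 4.

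**The case against.** The strongest reply is that no specified analysis is harmed. Sections 1.2 and 8.3 contain no aim, endpoint or model for expression, protein, miRNA or metabolism, and Section 6.2.3 defers at least part of that work. The blood analyses that the plan does name (COMT, candidate genes, GWAS) use germline genotype, which does not change with assignment. This stands, and it limits the point to future use of the samples. Such use is, however, the reason Section 6.2.3 gives for storing them.

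A second reply is that the text does not prove a late draw, and that a few minutes within one visit may mean nothing against a six-week change. This stands too. A reader might infer that the sample cannot serve as a baseline; the documents support only that it is not protected from assignment and disclosure.

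A reader might also infer that patients unhappy with their arm would decline the draw and so deplete the genetic analyses selectively, since Section 9.3 says: "If blood is not obtained at either Visit 1 or Visit 3, it will not be considered a protocol deviation/violation". The documents do not support this. That sentence classifies missing samples for administrative purposes and links refusal to no arm. No refusal rate is given. Blood is also drawn at Visit 3, so a patient missed at Visit 1 can still be genotyped unless both samples are missing. Section 8.3 in any case extracts DNA only from those who agree to it.

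Finally, drawing earlier is not wholly without cost. The clinician confirms the diagnosis and holds the envelopes, while the coordinator helps with the blood, so the new order adds a handover in the middle of the visit.

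**Conclusion.** The point holds in a limited form. Section 6.2.1 leaves the Visit 1 draw unprotected from assignment and from the arm-specific discussion, while Section 6.2.3 relies on that sample as the baseline for change. Change scores, and models that adjust for this sample, are exposed for expression, protein, miRNA and metabolic markers.

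The bias equals the between-arm difference in early shift, multiplied by the slope if the sample is a covariate. Its size cannot be estimated from the documents and may be zero. The values of f above are illustrations.

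Three things are not materially affected: the primary IBS-SSS analysis, because the questionnaires precede randomisation; the germline analyses, because genotype is fixed and a second draw is planned; and between-arm comparisons of Week 6 samples, which need no baseline. This is a worthwhile low-cost improvement, not a threat to the trial's main conclusions.

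**What to change.** Amend Section 6.2.1 by deleting the exception for blood, so that every Visit 1 assessment, blood included, is completed before randomisation. State that the draw takes place once eligibility is confirmed and before the envelope is opened. The visit, staff and tubes stay the same. Eligibility is already settled at that point, so no ineligible patients are bled. The cost is a small change in flow between clinician and coordinator.

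If the order cannot be changed, record the time of the draw relative to envelope opening, the discussion and the first dose.

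Label any samples already drawn after assignment as post-randomisation in Section 6.2.3 and in the data set. For those samples, make the between-arm comparison at Week 6 the main expression and metabolism analysis, with change from the first sample as supportive only.

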### 6.2.2 Follow-up Visits

**Visits 2 and 3:** At these visits, the following procedures will be performed: vital signs (Visit 3 only), brief physical examination with clinician interaction, dispensation of pills (if appropriate), pill counts (if appropriate), review of concomitant medications, and documentation of adverse events. A research coordinator will assist in completion of questionnaires and collection of blood. Whenever possible, the same treatment provider will see the patient for all visits.

Vital signs will not be recorded in the source documents, as they are done to mirror a standard clinic visit from the subject perspective and will not be analyzed.

### 6.2.3 Sample Collection

Genetic variation in genes encoding proteins involved in several neurotransmitter pathways has been shown to modify response to placebo treatment. This study will build on these findings to examine how placebo treatment modifies gene, protein and miRNA expression as well as changes in metabolism that may be associated with differential response to placebo treatment.

Although all these genomic studies will not be run in the primary study, it is important to collect samples that will allow these analyses to be done in the future. Aliquots of plasma, serum, white cells and red cells will be de-identified and stored at -80C. Samples will be collected at baseline and at the end of the study.

GWAS will be conducted to identify genes implicated in modifying placebo response.

#### **6.2.4 Blinding**

Blinding of the double-blind treatment groups will be maintained throughout the study by using procedures that are identical in method and appearance. The assessor who administered the questionnaires will be blinded to all groups. For patients randomized to either of the double blind administration groups, the clinician will be blinded to the treatment administered (peppermint oil or placebo).

The Investigator and study center personnel will not have access to the randomization code during the study except in the case of an emergency. Breaking the blind for a subject will only be done in the event of a medical emergency where the identify of study drug is necessary to appropriately treat the subject. If the blind is broken, the reason and date will be documented. Every attempt will be made to maintain the blind throughout the study.

#### **6.2.5 Completion/Final Evaluation**

Efforts will be made to complete data collection on all subjects regardless of compliance with treatment. Those who are not compliant will be noted.

There will not be any additional study procedures done for subjects that discontinue early.

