### 8.3 Analyses

All tests will be two-tailed with  $\alpha=.05$ . For our primary analyses, we will use a modified intention-to-treat analysis including any patient who was randomized and provided a baseline assessment and at least one post-baseline primary outcome assessment. We will also run per protocol analyses, and any substantive differences between the two methods will be reported.

We will examine the amount of missing data and the nature of the missingness (missing completely at random, missing at random, and missing not a random). If necessary, we will conduct a full intention to treat analysis.

**Aim 1.** To determine whether 6 weeks of open-label placebo, double-blind placebo and no-treatment results in different clinical outcomes. To test this aim, we will conduct a one-way analysis of covariance. In addition to treatment group, the model will include baseline IBS-SSS and stratification factors for gender and symptom severity.

Assuming that there is a significant difference between the 3 groups, Dunnett's analysis will be used to do pairwise analyses of the following aims

**1a.** To determine if 6 weeks of open-label placebo results in superior clinical outcome than no treatment control. Hypothesis: open-label placebo > no treatment control.

**1b.** To determine if 6 weeks of open-label placebo results in superior clinical outcome than double blind placebo. Hypothesis: open-label placebo > double-blind placebo.

**Secondary Aims Analysis Plan:** There are three secondary multi-disciplinary aims in this study.

**Secondary Aim 1 (Genetics Aim):** In our previous large RCT we found that the number methionine alleles in COMT val158met was associated with placebo responses especially to a combined placebo and supportive patient-provider relationship. We plan to confirm these findings and extend them by evaluating additional candidate genes implicated in placebo. Exploratory analyses will be performed in other candidate genes associated with placebo including: the mu-opioid receptor polymorphism (OPRM1 A118G), FAAH polymorphisms Pro129Thr. monoamine oxidase gene polymorphisms, and serotonin-related polymorphism CGTTLPR and G-703T (polymorphism in the tryptophan hydroxylase-2 (TPH-2) gene promoter).

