DNA will be extracted from those study participants who agree to the genetic screening and will be analyzed by a TaqMan allele discrimination assay. Subsequently, COMT and other candidate genotypes will be correlated with response to placebo or active drug treatment using the above mentioned outcomes. Furthermore, potential correlations of the COMT and other genotypes and patient-disease characteristics, for instance pain experience at baseline, will be examined.

**Secondary Aim 2 (Psychological Aim):** In our previous large RCT in IBS we found that higher levels of extraversion, agreeableness, and openness to experience are associated with increased response to placebo treatment, especially with an augmented patient-practitioner relationship. We will use the Five Factor Inventory (FFI) to measure these personality traits and

then use multiple regression to examine their association with outcomes after controlling for baseline severity.

**Secondary (exploratory) Aim:** To determine if 6 weeks of double-blind peppermint oil results in greater improvement than double-blind placebo in patients with IBS. Hypothesis: Double-blind peppermint oil > Double-blind placebo. To test this aim, we will conduct an analysis of covariance. In addition to treatment group, the model will include baseline IBS-SSS and stratification factors for gender and symptom severity.

**8.4 Power Calculations:** To estimate the effect size for Aim 1, we used our previous pilot trial in IBS. In that study, the effect size for the difference between open-label placebo and no-treatment on the IBS Symptom Severity Scale was  $d=0.53$ . For this comparison, there will be 88 patients in each group, and using ANCOVA to control for baseline scores leaves the power for the 3 group comparison at .96. To estimate the power for secondary (exploratory) aim using ANCOVA to control baseline scores leaves the power of .60; however, using more recent data that suggest an effect size of  $d=0.50$ , the power would be .78.

**8.5 Missing Data Minimization Strategies:** Missing data minimization strategies includes patient retention efforts and a modified intent-to-treat analysis. Each individual patient reported assessment will be captured electronically at each visit with missing responses prohibited by the electronic system.

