#### Instructions

These questions are designed to enable us to record and monitor the severity of your IBS. It is to be expected that your symptoms might vary over time, so please try and answer the questions based on how you currently feel (i.e. over the last 10 days or so). All information will be kept in **strict** confidence.

1. For questions where a number of different responses are a possibility please circle the response appropriate to you.
2. Some questions will require you to write in an appropriate response.
3. Some questions require you to put a cross on a line which enables us to judge the severity of a particular problem.

[figure not shown]
Please place your cross (X) anywhere on the line between 0-100% in order to indicate as accurately as possible the severity of your symptom.

This example shows a severity of approximately 90%.

1. Do you currently suffer from abdominal pain?  Yes  No

1b. If yes, how severe is your abdominal pain? *Please make an "X" anywhere on the line.*

1c. Out of 10 days, how many days do you experience abdominal pain? \_\_\_\_\_

2. Do you currently suffer from abdominal distention (bloating, swelling, or tightness)?

Yes  No

2b. If yes, how severe is your abdominal distention? *Please make an "X" anywhere on the line.*

### Appendix 3

List of Evaluations to be Completed at Each Visit

Paper Source Documents

Evaluation	Visit 1	Visit 2	Visit 3
Telephone screening			
Original signed ICF	X		
Physical Examination	X	X	X
Rome IV Diagnostic Criteria	X		
IBS-SSS	X	X	X
Visit 1 Template	X		
Visit 2 Template		X	
Visit 3 Template			X
Concomitant Medication Log	X	X	X
Adverse Event Log		X	X
Blood Collection	X		X

Entered Directly into RedCap

Evaluation	Visit 1	Visit 2	Visit 3
Rome IV Module	X		
Symptom Questionnaire		X	X
Why are you participating?	X		
IBS-ARS	X	X	X
IBS-GIS	X	X	X
Blinding Question		X	X
Expectancy Question	X		
Medication Adherence Questionnaire		X	X
Side Effects Questionnaire	X		X
PHQ-8	X		
GAD-7	X		
VSI	X		X
SF-12	X		
FFI	X		
CARE			X
PCS	X		X
BIDR			X
ISEL-12	X		X
Daily Questionnaire			

\* All questionnaires above are completed by the subjects. The demographic and Visit 1 IBS-SSS data in RedCap is completed by staff.

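### Section 6.2.5 can be followed so that early discontinuers give no week-6 IBS-SSS, and the analysis plan does not say how to handle the gap

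*Combined protocol and SAP*

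**What the plan says.** Section 6.2.5 opens with "Efforts will be made to complete data collection on all subjects regardless of compliance with treatment" and closes with "There will not be any additional study procedures done for subjects that discontinue early". It does not define discontinuation or say what counts as an additional procedure.

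The primary outcome is the IBS-SSS, with response defined in section 3.2 as "at least a 50 point decrease in their IBS-SSS from baseline to Visit 3", that is, at week 6. Appendix 3 schedules the scale at Visits 1, 2 and 3.

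The primary analysis in section 8.3 is a "modified intention-to-treat analysis including any patient who was randomized and provided a baseline assessment and at least one post-baseline primary outcome assessment". On missing data, section 8.3 says "We will examine the amount of missing data and the nature of the missingness" and then "If necessary, we will conduct a full intention to treat analysis". It names no trigger, imputation method or sensitivity analysis. Section 8.5 adds "Missing data minimization strategies includes patient retention efforts and a modified intent-to-treat analysis", together with an electronic block on unanswered items.

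**The concern.** The two sentences in section 6.2.5 pull in different directions, and the second is the one that a site can act on as an instruction. If it is taken to cover the remaining scheduled visits, the primary outcome at week 6 is not sought from the patients whose result is most in doubt.

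The rest of the plan does not make up for this. Choosing a modified ITT set collects no data; it leaves out the patients who have no post-baseline score. The electronic block deals with unanswered items within an assessment, not with a visit that does not take place. The retention efforts are not described. Examining the nature of the missingness cannot settle the matter either, because observed data cannot tell missing at random from missing not at random.

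The design makes this matter more than usual. Aim 1a compares two arms in which patients know what they were assigned, and Aim 1b compares a known with a concealed assignment. The outcome is self-reported. Leaving the study could plausibly depend both on arm and on lack of improvement, and that combination biases a comparison of those who remain.

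**Working it through.** **Step 1. Follow each type of patient through the rules** (sections 6.2.5 and 8.3, Appendix 3), with the closing sentence of 6.2.5 applied to all remaining visits.

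| Patient | Week-3 score | Week-6 score | In modified ITT set | Enters week-6 ANCOVA |
|---|---|---|---|---|
| Poor compliance, keeps attending | sought | sought | yes | yes |
| Discontinues before Visit 2 | none | none | no | no |
| Discontinues after Visit 2 | yes | none | yes | not stated |

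If the closing sentence rules out only an extra early-termination visit, the week-6 score could still be sought in the last two rows. The text does not say which is meant.

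**Step 2. Power.** Inputs from sections 8.3 and 8.4: 88 per group, d = 0.53, two-sided alpha .05, stated three-group power .96. The protocol gives neither the pattern of the three means nor the baseline correlation r, so both are assumed. The noncentrality is λ = n × Σ(μᵢ − μ̄)² / (1 − r²).

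- Means (0, 0, 0.53), r = 0: Σ = 0.187, λ = 88 × 0.187 = 16.5, power .960.
- Means (0, 0.265, 0.53), r = 0.5: Σ = 0.140, divided by 0.75 = 0.187, λ = 16.5, power .960.

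The stated .96 is reproduced under either assumption. The protocol gives no dropout rate; with an assumed loss of week-6 scores, equal in each arm:

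| Assumed loss | n per arm | Three-group power |
|---|---|---|
| 0% | 88 | .96 |
| 5% | 83.6 | .95 |
| 10% | 79.2 | .94 |
| 20% | 70.4 | .91 |
| 25% | 66 | .89 |

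For open-label placebo against no treatment alone, without covariate gain, the noncentral t has parameter 0.53 × √(n/2). At n = 88 this is 3.52 and power is .938; at n = 79 it is 3.33 and power is .912. Power is not the problem.

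**Step 3. Bias.** Let a proportion p of an arm be lost, and let those lost score g points worse at week 6 than those who stay. The mean of those who stay is then p × g better than the mean of the whole arm. With the same g in both arms, the bias in the difference is (p₁ − p₂) × g.

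Neither p nor g is in the documents. The assumed range for p₁ − p₂ is 5 to 15 percentage points. For g, 50 points is used only as a familiar distance on the scale, because it is the responder threshold in section 3.2; that threshold is a within-patient change, not a gap between groups.

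- 0.05 × 50 = 2.5 points
- 0.15 × 50 = 7.5 points
- With g = 100, the figures double to 5 and 15 points.

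The direction depends on which arm loses more non-improvers. Excess loss from no treatment makes that arm look better and shrinks the Aim 1a difference; excess loss from open-label placebo inflates it. Adjustment for baseline IBS-SSS would remove whatever part of g baseline explains. The protocol gives no standard deviation for the scale, so these figures cannot be converted to units of d.

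**The case against.** The strongest reply is that the two sentences can be reconciled. Patients in the no-additional-treatment arm have no study product to stop (section 5.1), so discontinuing early would naturally mean leaving the study. Under a heading about final evaluation, the closing sentence may rule out only an extra early-termination visit. A patient who stops the softgels but keeps attending is covered by the opening sentence. This reading is possible and stands as such, but the protocol does not state it, and sites should not have to infer it.

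A reader might go further and infer that week-6 scores are never collected from discontinuers and that a full ITT would therefore have no outcome data. The documents do not support either step. The opening sentence of 6.2.5 supports continued collection from non-compliant patients, who would have week-6 scores. Patients who leave after Visit 2 have a week-3 score, and eligibility requires a baseline score. A likelihood-based model or multiple imputation could use these. What is missing is any statement that one will be used, and either would rest on assumptions that observed week-6 scores would make less important.

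Three further points stand. The bias figures rest on assumed inputs. Section 8.5 does name retention efforts, which aim at the right target. Remote collection is not trivial: Appendix 2 has patients mark a cross on a line and Appendix 3 lists the IBS-SSS as a paper document, so a telephone call would not reproduce the instrument. The fix below takes account of this.

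**Conclusion.** The concern holds in this form: section 6.2.5 can be followed so that early discontinuers supply no week-6 IBS-SSS, and sections 8.3 and 8.5 do not say how the analysis would then proceed. Aims 1a and 1b are exposed to bias if the loss differs by arm and is related to outcome.

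The size is unknown. The 2.5 to 7.5 points are an illustration that assumes 5 to 15 percentage points of excess dropout, a 50-point gap common to both arms, no gain from baseline adjustment and no use of week-3 scores. If few patients leave, or they leave for reasons unrelated to symptoms, the bias is negligible. The loss of power is minor: about .96 to .94 for the three-group test at 10% loss. This is a worthwhile and cheap improvement, not a flaw that invalidates the design.

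**What to change.** Replace the closing sentence of section 6.2.5 with wording such as: *Subjects who stop study product or stop attending visits, and who have not withdrawn consent to data collection, will be asked to complete the IBS-SSS at the scheduled week-6 date, by mailed paper form or by a REDCap version that keeps the line-marking scale. No other procedures are required. The mode of completion will be recorded.* This covers the no-treatment arm and separates stopping product from withdrawing consent.

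Include these scores in the analysis of all randomised patients. Under the existing definition, a week-6 score obtained this way would also bring a patient who left before Visit 2 into the modified ITT set.

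In section 8.3, define the full ITT analysis: when it is run, who is in it, how a patient with only a week-3 score or no post-baseline score is handled, and which sensitivity analysis accompanies it.

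The cost is one five-item questionnaire per early discontinuer, a REDCap version or postage, and a short amendment. Some scores will be collected remotely, so mode will differ between discontinuers and completers, and some people who stop attending will not reply.
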